8.2 Vulnerable Populations

Pregnant women, those who lack consent capacity, the mentally ill, prisoners, cognitively impaired persons, non-English speaking individuals and children will not be included in this research study.

Employees of the clinics that agree to participate in this study will be enrolled, but these individuals do not have a status relationship with members of the research team that would constitute a vulnerable population.

8.3 Participant Identification

8.3.1 Clinic Identification

The pilot will take place in three rural clinics: UW Health Family Practice Clinic in Belleville, Sauk Prairie Healthcare Diabetes Clinic, and Sauk Prairie Healthcare Wound Care Clinic.

8.3.2 Healthcare Worker Identification

Healthcare workers will be identified through their employment at each of the three rural clinics participating in the study. Lists of eligible employees will be obtained from clinic administrators.

8.3.3 Patient Participant Identification

Following identification of healthcare workers, the medical records of the participating clinics will be reviewed to identify patients with diabetes who are cared for by a participating healthcare worker. Those who develop a diabetic foot ulcer will further be identified by participating rural providers in the course of their normal work flow and referred to the research coordinators. Additionally, the research coordinators will monitor clinic schedules of participating rural providers to identify incoming patients with new foot ulcers.

8.4 Subject Recruitment

A total of 45 patient participants and up to 30 healthcare workers will be recruited from the 3 rural clinic sites in Wisconsin. Recruitment will be staggered so that Clinic 1 will be active for 24 months with a target patient enrollment of 20; Clinics 2 and 3 will be active for 18 months with a target patient enrollment of 25 total. This translates into a targeted rate of enrollment of 4.5 patients per activated clinic every 6 months. The initial recruitment strategy outlined below will be used to recruit patient participants from the first clinic. Recruitment strategies will be iteratively adapted one month prior to enrollment of the second and third clinics, and again at the end of the pilot. Changes to recruitment will be submitted to the IRB prior to implementation, as needed. Specific recruitment strategies are as follows:

8.4.1 Healthcare Worker Recruitment

Approximately one month prior to activating each clinic for patient enrollment, healthcare workers at each respective clinic will receive an email invitation to an informational meeting regarding the study. Up to three emails may be sent in the four weeks prior to the meeting with an opt-out option included in each email. The meeting will take place when patients are not scheduled and include light fare (e.g., pizza). The principal investigator and study coordinator will present details of the study. The email invitation will offer individual recruitment meetings for those interested in participating but unable to attend the dinner meeting. Attendees will be invited to register for a 1:1 interview to improve the recruitment session, regardless of their decision to participate in the pilot as part of purposeful sampling to obtain qualitative data on improving the recruitment process for healthcare workers.

8.4.2 Patient Participant Recruitment

8.4.2.1 UW Health Family Practice Clinic in Belleville

Potentially eligible patients at UW Health Family Practice Belleville clinic will be identified by the Clinical Research Data Service and provided on a weekly basis to the study team so that eligibility can be confirmed before patients are approached at the clinic. Providers can also refer patients directly to the study team. The clinic will be offered the option of introducing the study with information sheets in the waiting areas, such as a table top flyer and bi-fold brochure (see Appendix).

8.4.2.1 SPH Clinics

The study team will review upcoming clinic schedules one week in advance to identify potentially eligible patients using the SPH EHR. A Business Associates Agreement will be in place to formalize UW study team's remote access to SPH EHR. Providers can also refer patients directly to the study team. The clinic will be offered the option of introducing the study with information sheets in the waiting areas, such as a table top flyer and bi-fold brochure (see Appendix).

Telephone Contact: Research coordinators from the University of Wisconsin without clinical ties to the clinic or healthcare worker participants will review primary care provider schedules weekly to identify patients being seen for a diabetic foot ulcer. We anticipate that most patients will be identified very soon after the initial diagnosis, although some delay may occur between diagnosis and identifying these patients by the research coordinators during subsequent follow up. Additionally, rural providers will be able to directly contact the research coordinators when they identify a potentially eligible patient. After checking with the rural providers to ensure identified patients are eligible (i.e. not on hospice, truly have a diabetic foot ulcer), coordinators will telephone potential patient participants, using the preferred contact number listed in the clinic system. Patients will receive up to three calls on separate days and different times (morning, mid-day, and afternoon). If a call is not answered, coordinators will leave a message inviting the participant to return the call. When contact is made, coordinators will offer an in-person face-to-face meeting to review eligibility, provide detailed information on the study, and obtain written consent. The standardized telephone script is available in the Appendix. Patients contacted by telephone, regardless of their decision to further engage in the pilot, will be asked if they are willing to participate in a future interview to improve the recruitment process.

See section 11.0 for additional information on adaptive recruitment strategies.

8.5 Remuneration and Retention Strategies

8.5.1 Retention Strategies

We will request feedback on communication throughout the study to ensure both formal and informal communications are clear and as part of the adaptive design process for retention (i.e. we will use feedback to improve recruitment and retention protocols before activating additional clinic sites and at the end of the study). The following initial retention strategies will be implemented, with revised strategies (in *italics* below) added as developed:

- Our research coordinator will meet weekly with participating healthcare workers to review patient enrollment and assess, but not facilitate, use of the care algorithm/referral checklist.
- Researchers will solicit formal feedback from both healthcare worker and patient participants during planned interviews and preliminary data (e.g. up-to-date recruitment and retention rates) will be shared during the interviews.
- We will invite two research participants, optimally one healthcare worker and one patient, from each activated clinic to participate in the final co-design session with the Cooperative, incorporating on-the-ground patient and healthcare worker perspectives.
- All enrolled patients and healthcare workers will receive emailed or mailed (per participant preference) study updates linking recruitment and retention changes to participant feedback after each adaptation and at the close of the study. Healthcare workers may also receive in-person study updates at standing meetings if that is their clinic's preference.

- *All enrolled patients will be mailed an informational letter describing the study no earlier than 1 month after consent. The purpose of this letter is to remind patient participants about the study, including its purpose, and serve as a way to keep them feeling engaged about the project. This retention strategy emerged from our qualitative interviews to improve study retention. The form letter has been added to the appendix.*

See section 11.0 for additional information on adaptive retention strategies.

8.5.2 Remuneration

Individual healthcare workers will not receive financial compensation for participating in the pilot. Rather, the clinics will be compensated \$4500 for their involvement. We doubt this nominal fee (compared to their overall operating budgets) will be enough to risk coercion from clinic managers to healthcare workers to participate. Patient participants who consent will be given \$100 upon enrollment and an additional \$100 upon completion of the 3-month follow-up. This has been in the form of cash for most of the duration of the study. However, starting in 2025, per UW-Madison policy, stipends for research participation must be paid using the Advarra payments system. Within this system, participants have the choice of a Visa card, direct deposit, or check. Enrollment will be completed in 2024 and payment for completion of the study is paid via mail. Since will be unable to work with the patient participants in person for this payment, and due to the nature of our patient participant demographics (majority elderly, several without email and/or limited access to internet/computers and/or transportation), we will be opting to send payment to all patient participants who complete the study in the form of a Visa card. Patient participants enrolled after 9/23/24 will be notified that although their enrollment payment is in the form of cash, they should expect payment for completion of the study in the form of a Visa card due to university policy changes. Patient remuneration may be revised as part of co-design adaptations.

8.6 Early Termination and Withdrawal

All subjects are free to withdraw from participation in the study at any time upon request via letter as described on the consent form.

The Principal Investigator (PI) may discontinue or withdraw a healthcare worker from the study at her discretion for failure to consider use of the integrated care model with their patient participants, although deviation from the model will be allowed based upon the rural provider's clinical judgement.

Patient participants who sign the informed consent form, receive the study intervention, then subsequently withdraw, or are withdrawn or discontinued from the study will not be replaced.

The following actions will be taken if a patient participant withdraws or fails to return the three month follow-up phone call:

- Before a patient participant is deemed lost to follow-up, the investigator or designee will make every effort to regain contact with the participant where possible, by completing up to 3 telephone calls. These contact attempts shall be documented in the participant's study file. Participants that do not agree to participate in the follow-up phone call will be asked to provide a reason for discontinuing participation.
- If the patient participant continues to be unreachable, they will be considered to have withdrawn from the study with a primary reason of lost to follow-up. The withdrawn date is the last day of attempted contact.

9.0 INTEGRATED CARE MODEL INTERVENTION

9.1 Integrated Care Model

The integrated care model uses two tools to promote provider collaboration across rural and urban healthcare systems: 1) a care algorithm and 2) a referral checklist.

The care algorithm will be used by rural providers—primary care providers (PCPs) at UW Health Belleville clinic and rural diabetes and wound care specialists at SPH clinics—to guide integrated care for patients with diabetic foot ulcers (see Appendix). It supports rural providers, allowing most patients to be cared for locally and reserving urban specialty referral for those with limb-threatening disease. The algorithm triggers intensive medical management, especially for key gaps in vascular care. The rural providers will retain final clinical decision making autonomy; the algorithm is there as a general guide and clinical support tool with the ability to deviate from the algorithm when it is in the best interests of the patient. The model also supports rural patients by allowing both in-clinic and telemedicine urban specialty consultation. Rural patients and urban specialists jointly decide between in-person and telemedicine consultation for each visit.

The integrated care model's referral checklist will be used by rural schedulers who place referrals to urban specialists (see Appendix). It prompts schedulers to fax appropriate supporting documents (e.g., notes, labs, vascular testing results) with the referral request.

10.0 INTEGRATED CARE MODEL STUDY VISITS AND PROCEDURES

10.1 Healthcare Workers

10.1.1 Screening and Enrollment

10.1.1.1 Informed Consent

For healthcare workers participating in the informational meeting session, the PI and study coordinator will present details of the study to the group. Consent forms will be distributed to the group for review during the session. Participants will have time to ask questions during the group session or after the session is complete. Those willing to participate can sign and date the consent during the meeting. Having the rural providers and schedulers attend the same informational meeting is beneficial because it is efficient. The consents will be turned in without eliciting any formal knowledge of who signed or not, minimizing risk of coercion.

For healthcare workers unable to attend the informational meeting session, the PI or study coordinator will meet with the participant to discuss the study. The consent form will be provided to the subject for review and the PI or study coordinator will give the subject time to review and ask questions. If the subject is willing to participate, they can sign and date the consent form at that time. Immediately following signed informed consent, self-reported demographics will be collected using a standardized form to comply with NIH sponsor requirements.

All healthcare workers will be provided with the option to take the consent form home with them for additional consideration and to contact the study PI or research coordinators with additional questions. The study PI or a research coordinator will review all informed consent documents to ensure that all fields that require a response are completed. Each participant will be provided with a copy of the consent form to keep for their records. Original copies of the consent form will be retained by the study PI and research coordinators.

10.1.1.2 Eligibility Confirmation Screening

After informed consent is obtained from healthcare workers, screening will be performed to ensure an appropriate match between enrolled rural providers and schedulers. Healthcare workers will be excluded if the clinic manager determines there is insufficient overlap in work schedules between rural providers and schedulers. In the event a healthcare worker is excluded, they will be thanked for their interest and offered the opportunity to receive updates on the status of the study. Healthcare workers may also be approached for participation in recruitment and retention interviews.

10.1.2 On-Study and Follow-up Procedures

Healthcare workers will meet with the PI or a research coordinator to discuss the integrated care model in detail. Rural providers will be provided with a copy of the care algorithm and schedulers will be provided with a copy of the referral checklist to review. Healthcare workers will be encouraged to ask questions about the integrated care processes. Once eligible patient participants are identified, rural providers and schedulers will be informed of the patient participant's enrollment in the trial. If a patient is enrolled through a Sauk Prairie Healthcare Clinic (diabetes or wound care clinics), an email will be sent to the patient's PCP informing them of the patient's enrollment in the study. A research coordinator will meet with rural providers and schedulers weekly to discuss the status of the study and answer any questions they may have. The PI will be available as back-up to answer any questions.

10.2 Patient Participants

10.2.1 Study Calendar

The procedures performed at each study visit are listed in the table below.

Procedure	Screening	Baseline visit	Intervention	Telephone contact	End of Study/Early Withdrawal
Visit Window	Identification of Foot Ulcer	Next Clinic Visit		Month 3	
Telephone Screen	X				
Informed Consent		X			
Eligibility		X			
Integrated Care Model			X		
Chart Review		X	X	X	X
Follow-up				X	

10.2.2 Screening and Enrollment

10.2.2.1 Pre-screening

Research coordinators will review the schedules of participating rural providers weekly to identify patients being seen for a diabetic foot ulcer. Additionally, rural providers will be encouraged to contact the research coordinators when they identify a potentially eligible patient. To assist with this process, providers will have access to a bi-fold brochure generally introducing the study and table top flyers to display in patient waiting rooms (see Appendix) For the UW Health Family Medicine Clinic in Belleville, CRDS will also generate a data report to help screen for potentially eligible patient participants. The report will be delivered via REDCap to the study team weekly and cover the upcoming week's schedule. Once identified, telephone screening will be performed for initial eligibility and to schedule the consent discussion. The telephone script to screen for eligibility is available in the Appendix.

10.2.2.2 Informed Consent

Preliminarily eligible patient participants will be invited to participate in an informed consent discussion and formal screening at their next scheduled clinic visit. Potential patient participants are asked to come to the visit immediately after their scheduled clinic visit. The informed consent process will be conducted following all federal and institutional regulations relating to informed consent. The discussion will take place in a private room at the rural provider's clinic. Informed consent will be obtained prior to conducting any study-related activities. Immediately following signed informed consent, self-reported demographics will be collected using a standardized form to comply with NIH sponsor requirements.

The informed consent process will be performed as follows:

- A trained research coordinator will review the informed consent form and discuss the study in detail with the potential research participant.
- A trained research coordinator will explain the study, its risks and benefits, what would be required of the research participant, and alternatives to participation.
- The research participant will be given the opportunity to take the informed consent form home so that they may discuss it with family members, friends, clergy, or others when possible.
- The research participant will have the opportunity to ask questions and have all questions answered by the research coordinator.
- The informed consent document must be signed and dated by the research participant.
- A trained research coordinator will review the informed consent document to ensure that all fields that require a response are complete (i.e., checkbox marked yes or no, etc.) as applicable.
- The research participant will be given a copy of the informed consent form. The original signed and dated informed consent form is kept with the study records.

10.2.2.3 Baseline Visit and Enrollment

Following informed consent, subject eligibility will be confirmed as follows:

A patient participant will be defined as "enrolled" in the study when they meet the following criteria:

- The patient participant has been consented by a research coordinator.
- The patient participant and a research coordinator have completed all screening documentation.
- The PI has verified that the patient participant meets all of the inclusion criteria.
- The PI has verified that patient participant meets none of the exclusion criteria.
- The patient participant completed a clinic visit with the participating rural provider, who considered recommendations outlined in the integrated care algorithm.

Following enrollment, the participant's medical record will be reviewed, and patient characteristic data will be abstracted. This will include sociodemographic data, comorbidities, medications, lab values, and ulcer characteristics. See Appendix for full list of variables.

10.2.2.4 Screen Failure and Re-enrollment

Individuals who do not meet the criteria for participation in this trial (screen failure) because they are determined not to have a diabetic foot ulcer may be rescreened if they develop a diabetic foot ulcer later. Rescreened patient participants should be assigned a new subject ID number when they are re-screened.

10.2.3 On-Study and Follow-up Procedures

10.2.3.1 Integrated Care Model Visit

Integrated Care Model activities will be performed by the rural provider and scheduler following the patient participants' enrollment in the study, as outlined above.

Following the rural provider visit, data on care processes will be abstracted from the participant's medical records. This includes information related to vascular disease care processes, infectious disease care processes, and other care processes. See Appendix for the full list of variables.

10.2.3.2 3 Month Follow-up

Patient participants will receive a follow-up call 3 months after their integrated care model visit (i.e., enrollment) to assess ulcer status and screen for any adverse events. This will be done by a research coordinator. Additionally, data will be abstracted from the patient's medical records. This includes medications, lab values, ulcer characteristics, and details of major or minor amputation, if applicable. If the patient participant is deceased at the time of the 3-month follow-up, information about the participant's death will also be obtained from medical records. See Appendix for the full list of variables. The following is a list of adverse events that will be tracked by the study team:

- Hypoglycemia requiring hospitalization or an emergency room visit
- Adverse reaction to a smoking cessation product
- Muscle aches after starting or changing a statin
- Complication of a revascularization procedure
- Adverse reaction to a wound care product or dressing
- Adverse reaction to an antibiotic prescribed for an infection complicating the diabetic foot ulcer
- Hospitalization for a diabetic foot ulcer (occurs in 30% of patients with diabetic foot ulcers)
- Major (above-ankle) amputation (risk increases with ulcer severity but is 5% in the overall national cohort of patients with diabetic foot ulcers)
- Death
- Patient reported adverse events that the patient attributes to study participation

All serious, unanticipated adverse events, deaths (whether anticipated or not), and major amputations (whether anticipated or not) will be reported to the ICTR DMC within 14 days of the study team becoming aware of these events.

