10.3.2 Data Abstraction

Medical records will be reviewed, and similar data collected from prospectively enrolled patient participants will be extracted from historical control patient participants. This includes sociodemographic data, comorbidities, medications, lab values, and ulcer characteristics at baseline and at 3 months post-baseline. Amputation and death data will also be collected, if applicable. See Appendix for the full list of variables.

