15.2 Safety Oversight

Safety oversight will be under the direction of a Data and Safety Monitoring Board (DSMB) composed of individuals with the appropriate expertise, including rural providers and specialists. Members of the DSMB should be independent from the study conduct and free of conflict of interest, or measures should be in place to minimize perceived conflict of interest. The DSMB will meet at least semiannually to assess safety and efficacy data on each arm of the study. The DSMB will operate under the rules of an approved charter that will be written and reviewed at the organizational meeting of the DSMB. At this time, each data element that the DSMB needs to assess will be clearly defined. The DSMB will provide its input to the PI and funder (NIDDK).

The ICTR DMC will provide an independent biostatistician to create reports of overall data analysis preparation for review by the DMC for bi-annual meetings.

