18.10 Appendix 10: Integrated Care Model Chart Review Variables

Patient characteristics	Sociodemographics	Age, sex, race, marital status, area deprivation index, insurance, clinic 1-3, primary care provider, all assessed at baseline
	Comorbidities	Charlson comorbidity index, hypertension, hyperlipidemia, coronary artery disease, stroke/TIA, peripheral vascular disease, end-stage renal disease, peripheral neuropathy, Charcot arthropathy, body mass index, smoking status, all assessed at baseline
	Medications	Use of anticoagulant, angiotensin reductase inhibitor, angiotensin II receptor blocker, all assessed at baseline and 3-month follow-up
	Lab values	Hemoglobin A1C, serum creatinine, both assessed at baseline and 3-month follow-up
	Ulcer characteristics	Date of diagnosis, Wagner severity ¹⁰⁴ grade at baseline and 3-month follow-up
Care processes	5 Vascular disease care processes	
 1) Baseline exam documents pedal pulse assessment 2) Baseline visit documents smoking status and cessation counseling within 3-months if indicated 3) Baseline visit documents statin use, and started within 3-months if indicated 4) ABI completed in 1 week for patients with decreased/absent pulses 5) Patients with ABIs ≤0.7 seen by vascular surgery within 2 weeks
	4 Infectious disease care processes	
 1) Baseline plain films for serial assessment of osteomyelitis 2) All exams document the presence/absence of findings suggestive of infection 3) Initial soft tissue infections treated with 2 weeks of broad spectrum antibiotics 4) Patients with concerns of, deep space abscess or osteomyelitis referred to a surgeon and/or infectious disease consultation in 2 weeks
	Other care processes	ABI results, referral to additional consultants (e.g., podiatry), whether vascular surgery and infectious disease consults were in-person or via telehealth, whether vascular surgery or infectious disease consults were never scheduled, canceled, or no-shows, all assessed at 3-month follow-up
	Ulcer status	Healed, ulcerated, major or minor amputation at 3 months, assessed by chart review for all patients & by patient report for those receiving integrated care
	Death	Patient died within the 3-month follow-up

18.11 Appendix 11: Phone Script for Recruitment of Participants for Qualitative Recruitment Interviews

Recruitment Telephone Script for Qualitative Recruitment Interviews

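### Seven of the nine tracked adverse events that a chart could show have no chart-review field in either arm, so the by-arm safety review is limited to amputation and death

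*Combined protocol and SAP*

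**What the plan says.** Section 10.2.3.2 describes a month-3 call to active patients "to assess ulcer status and screen for any adverse events. This will be done by a research coordinator". It then turns to the chart abstraction at the same time point: "This includes medications, lab values, ulcer characteristics, and details of major or minor amputation, if applicable". If the patient has died, information about the "death will also be obtained from medical records". The same section introduces the ten events with "The following is a list of adverse events that will be tracked by the study team", without naming a data source for each; section 14.2 repeats the list.

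Historical controls are chart review only. Section 10.3.2 lists sociodemographics, comorbidities, medications, laboratory values and ulcer characteristics, then adds: "Amputation and death data will also be collected, if applicable". Both sections send the reader to the Appendix for the complete variable list.

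Appendix 10 has a row for ulcer status, including amputation, "assessed by chart review for all patients & by patient report for those receiving integrated care", and a row for death: "Patient died within the 3-month follow-up". It has no row for any other tracked event.

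Section 15.2 states: "The DSMB will meet at least semiannually to assess safety and efficacy data on each arm of the study".

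**The concern.** Section 9.1 says that the algorithm prompts more intensive medical management. Several of the listed events (hypoglycemia, drug and dressing reactions, revascularization complications) are plausible harms of such management, so they are the events on which a safety review would want information from both arms.

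As described, they are collected from three-month patient recall, in active patients who are alive and answer the phone. A low count could reflect missed events. A high count could not be separated from background, because controls have no described source for these events. The only outside benchmark is the 30% figure for ulcer hospitalization, which carries no stated follow-up time.

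**Working it through.** **Event count.** The ten events in 10.2.3.2 and 14.2, set against the chart variables in 10.2.3.2, 10.3.2 and Appendix 10:

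| Tracked event | Could a chart show it? | Chart field, active | Chart field, control |
|---|---|---|---|
| Hypoglycemia with hospital or ER visit | yes | none | none |
| Smoking-cessation product reaction | yes | none | none |
| Statin muscle aches | yes | none | none |
| Revascularization complication | yes | none | none |
| Wound product or dressing reaction | yes | none | none |
| Antibiotic reaction | yes | none | none |
| Hospitalization for the ulcer | yes | none | none |
| Major amputation | yes | present | present |
| Death | yes | present | present |
| Event the patient attributes to the study | no | none | none |

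10 − 1 = 9 are chart-visible. 9 − 2 = 7 have no field in either arm.

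**Who is left out.** There are 27 active patients (13.2) and 162 − 27 = 135 controls. For the seven events, no source is described for any control. An active patient who died, or was not reached after up to three calls (8.6), gives no call data. The study calendar (10.2.1) nevertheless has chart review at month 3 and at early withdrawal.

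**Possible size in the active arm.** The plan gives no computed figure to reproduce here and no dropout rate. The following are assumptions: a 30% ulcer hospitalization rate (the benchmark in 10.2.3.2, taken as if it applied to three months) and 10% or 20% not reached (20% is the complement of the 80% retention goal).

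- Expected hospitalizations: 27 × 0.30 = 8.1.
- 20% not reached: 27 × 0.20 = 5.4 patients. Random loss: 8.1 × 0.80 = 6.5 found. Worst case, all unreached patients hospitalized: 8.1 − 5.4 = 2.7 found, or 2.7/21.6 = 12.5% of those reached.
- 10% not reached: 27 × 0.10 = 2.7 patients. Random loss: 8.1 × 0.90 = 7.3 found. Worst case: 8.1 − 2.7 = 5.4 found, or 5.4/24.3 = 22.2% of those reached.

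**What chart fields in both arms would allow.**

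- Active arm alone, 8 of 27 hospitalized: Clopper-Pearson 95% interval 13.8% to 50.2%, about 18 points on either side.
- Difference between arms, 30% assumed in both, matching ignored: 1.96 × √(0.3 × 0.7 × (1/27 + 1/135)) = 0.189, about 19 points.
- Power against 30% in controls (27 versus 135, two-sided 0.05, matching ignored): 0.52 if the active rate is 50%, 0.84 if it is 60%.

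The second margin is no tighter than the first. The gain is a common data source and a window of equal length in patients of the same clinics, not precision.

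**The case against.** The strongest reply is that the gap is read from silence. Section 10.2.3.2 says that the study team tracks the events and does not confine the source to the call. Charts are opened at several points, the telephone script tells patients that their chart is followed for three months, coordinators meet providers weekly, and controls are to have data similar to those of active patients. Case report forms are not reproduced, and 15.2 leaves the data elements to a DSMB charter that we cannot see.

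Part of this stands. The documents do not show that the seven events will never be recorded, and staff may learn of some by other routes. But 10.2.3.2 and 10.3.2 both treat the Appendix as the full variable list, and the events are not on it. Where two sources are meant, as for ulcer status, Appendix 10 says so. A charter cannot supply control data that nobody abstracts.

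A reader might infer more than the documents support:

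- That no safety review by arm is possible. Major amputation and death can be compared from charts now, and the stopping criteria in 14.2 and 15.1 rest on major amputation.
- That the sickest patients drop out. Nothing links dropout to severity. Sick patients may be over-represented among those not reached, but death and amputation do not depend on the call. An unreachable patient's withdrawal date is the last contact attempt (8.6), and data up to that date are kept unless the participant asks otherwise (12.4.8).
- That a fifth of patients will be lost. The 80% is a goal, not an expected rate.
- That abstracting controls would supply a concurrent comparator. Controls are historical and are sought backward in time until the number is reached (10.3.1).

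**Conclusion.** The concern holds in a limited form. Seven of nine chart-visible tracked events lack a chart field in either arm, and the only described screen for them is the active patients' month-3 call. The by-arm review in 15.2 is therefore limited to amputation and death, and events may be missed in active patients who died or were not reached. The count follows directly from the documents. The size of any under-count does not: 6.5 or 2.7 found of 8.1 depends on the assumed 30% and 20%. The primary and secondary endpoints are unaffected. The change is worth making because it is cheap, can be done after enrollment has closed, and widens what the safety review can say.

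**What to change.** Add three yes/no-plus-date fields to the 3-month chart abstraction in Appendix 10, 10.2.3.2 and 10.3.2, for both arms: hospitalization for the ulcer, hospitalization or ER visit for hypoglycemia, and revascularization complication. These are the events most likely to be charted; milder reactions are less dependable there.

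Complete the fields for all historical controls, and for active patients whether or not the call was made, within the consent-withdrawal limits in 12.4.8. Use the chart as the common source for the between-arm safety table, and label it a historical, not concurrent, comparison. Report call-only events descriptively for the active arm, with completed calls as the denominator. Reword 15.2 so that by-arm review covers only events abstracted in both arms.

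The cost is three fields in about 162 charts, possibly reopening some already abstracted, plus a short amendment and a check that the control waiver covers the new fields. Under-capture of outside admissions may remain in both arms: abstractors have the three clinics' records (12.1.1), and 5.4.1 itself describes disjointed electronic records as a barrier.
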